### 3 PROTOCOL SUMMARY

Protocol Number:	3333934_C
Protocol Title:	ASSURE WCD Clinical Evaluation – Conversion Efficacy Study (ACE-CONVERT)
Study Population:	Patients who are scheduled for any of the procedures specified in Inclusion Criterion 3 (below).
Study Design:	Multicenter single arm open label
Number of Subjects:	20
Study Sites:	Subjects will be enrolled at up to 5 clinical sites in the United States where procedures specified in Inclusion Criterion 3 (below) are routinely performed. There is no minimum or maximum number of subjects that may be enrolled at each site.
Eligibility Criteria:	
Subjects who meet all Inclusion Criteria and no Exclusion Criteria may be enrolled in the study.
 
Inclusion Criteria:
 

1) Males or females, age <math>\geq</math> 18 years

2) Able and willing to provide written informed consent before undergoing any study-related procedures

3) Scheduled for any of the following procedures:

a) Electrophysiology study for induction of ventricular arrhythmias

b) Non-invasive electrophysiology testing using an existing implantable defibrillator

c) ICD replacement procedure during which induction of a ventricular arrhythmia is planned

d) Ablation of ventricular tachycardia (patients undergoing ventricular tachycardia ablation in which ONLY a substrate modification approach is planned, with no intention of inducing a ventricular arrhythmia, should not be included)

	
Exclusion Criteria:
 

1. Any condition that by the judgement of the physician investigator precludes the subject's ability to comply with the study requirements

2. Pregnancy

3. Use of mechanical circulatory support (e.g. LVAD, Total Artificial Heart, intraaortic balloon pump or Impella)

4. Documented nonchronic cardiac thrombus

5. Atrial fibrillation or atrial flutter without therapeutic systemic anticoagulation

6. Critical aortic stenosis

7. Unstable coronary artery disease (CAD)

8. Recent stroke or transient ischemic attack (TIA)

9. Hemodynamic instability

10. Currently implanted Boston Scientific S-ICD (due to location of implant relative to test system)

11. Unstable angina

12. New York Heart Association (NYHA) Class IV

13. Left Ventricular Ejection Fraction (LVEF) < 20%

14. Any medical condition that by the judgement of the physician investigator, patient participation in this study is not in the best interest of the patient

15. History of difficulty of ventricular arrhythmia induction

16. Amiodarone use within 3 months before the study procedure

Investigational Therapy:	ASSURE 170 Joule biphasic defibrillation waveform
Energy Delivery Protocol:	Up to two 170 Joule shocks will be delivered from the Test System. If the second shock is unsuccessful, additional rescue shocks will be delivered using a commercially available internal or external defibrillator.
Study Procedures:	Cardiac patients will be screened for eligibility by the clinical site staff members in advance of the procedure date. Eligible patients will be provided the informed consent form and will be allowed enough time to review the consent, and have any questions adequately addressed. Only patients who provide written informed consent to participate will be enrolled as study subjects. Conscious sedation or general anesthesia will be administered per investigator preference. Participating subjects will have two sets of commercially available disposable adhesive defibrillation pads applied in advance of the procedure. One set will be placed in defined locations and used to deliver the experimental defibrillation shock using the Test System. The other pair will be located on the subject's torso according to physician preference and will be attached to a commercially available external defibrillator for backup rescue defibrillation. Backup rescue defibrillation can

	
also be done using an internal defibrillator per the physician preference. Commercially available ECG monitoring electrodes will be positioned as needed. The ASSURE WCD Monitor will be configured to Manual Shock mode, which allows the experimental shock to be delivered by a Kestra Clinical Specialist on command of the physician Investigator or Sub-Investigator.
 
A single sustained episode of rapid VT or VF will be induced during an electrophysiologic study from a catheter or an implanted defibrillator or may occur spontaneously. If the Arrhythmia is > 150bpm, then a 170J shock will be delivered from the Test System to convert the arrhythmia. A second shock at 170J will be delivered from the Test System if the first shock is unsuccessful.
 
Further rescue shocks may be delivered via an internal or external defibrillator at the Investigator's discretion.
 
Conversion is defined as the presence of a non-shockable rhythm after shock delivery. Documentation that will be collected includes captured screen shots and log files from the Tablet programmer, paper copies of ECG strips from the EP monitoring system, and a study-specific physician procedure report.

Efficacy Objective: Primary Endpoint: Secondary Endpoint:	To evaluate conversion efficacy of the ASSURE WCD Waveform Estimated cumulative first and second shock VT/VF conversion efficacy $\geq 94\%$ First shock VT/VF conversion efficacy (report only)
Safety Objective: Safety Endpoint:	To collect information on adverse events at least possibly related to use of the investigational Test System Summary of adverse events that are at least possibly related to use of the investigational Test System, including classification of Unanticipated Adverse Device Effects
Study Duration:	Individual subject participation is during acute intra-procedural testing only. Subjects can be enrolled only once. Total Study Duration from first subject in to last subject out will be approximately two months.

## 4 GLOSSARY OF ABBREVIATIONS AND DEFINITION OF TERMS

ABBREVIATION	DEFINITION
AADE	Anticipated Adverse Device Effect
ADAM	ASSURE Defibrillation Adapter Module
AE	Adverse Event
AED	Automated External Defibrillator
CAD	Coronary Artery Disease
CFR	Code of Federal Regulations
CIED	Cardiac Implantable Electronic Device
CPVT	Catecholaminergic Polymorphic Ventricular Tachycardia
CRA	Clinical Research Associate
CRF	Case Report Form
CRO	Contract Research Organization
ECG	Electrocardiogram
EPS	Electrophysiology Study
FPI	First Patient In
FDA	Food and Drug Administration
GCP	Good Clinical Practice (Guidelines)
GDR	General Document Record
ICD	Implantable Cardioverter-Defibrillator
ICF	Informed Consent Form
ICH	International Conference on Harmonisation
IEC	International Electrotechnical Commission
ILR	Implantable Loop Recorder
IRB	Institutional Review Board
LPO	Last Patient Out
LVAD	Left Ventricular Assist Device
LVEF	Left Ventricular Ejection Fraction
MI	Myocardial Infarction
PP	Per-Protocol
PEA	Pulseless Electrical Activity
SAE	Serious Adverse Event
SCA	Sudden Cardiac Arrest
S-ICD	Subcutaneous Implantable Cardioverter-Defibrillator
TIA	Transient Ischemic Attack
UADE	Unanticipated Adverse Device Effect
VF	Ventricular Fibrillation
VT	Ventricular Tachycardia
WCD	Wearable Cardioverter Defibrillator

## 5 INTRODUCTION

### Background

The Wearable Cardioverter-Defibrillator (WCD) is indicated for adult patients who are at risk of sudden cardiac arrest (SCA) and are not immediate candidates for or decline an implantable defibrillator. The study Sponsor has developed a new wearable defibrillator, the ASSURE WCD, to address this clinical situation.

The ASSURE WCD uses a biphasic truncated exponential waveform to deliver 170 Joules from a 140 $\mu$ F capacitor. The waveform is like that used by existing commercially available devices, including Physio-Control LifePak12®, the Philips Heartstart® Automated External Defibrillator (AED), and the ZOLL LifeVest® Wearable Cardiac Defibrillator (APPENDIX A).

This study is part of a comprehensive set of evaluation protocols which has been proposed to establish safety and effectiveness of the ASSURE WCD and will be included in support of the Premarket Approval (PMA) application for the ASSURE WCD.

### Rationale for Approach

Defibrillation efficacy testing was once considered a standard part of ICD implantation. Decades of clinical experience with biphasic waveforms and other significant improvements in ICD technology over the years raised the question of the value of routine defibrillation testing resulting in the initiation of several large, prospective randomized controlled studies. Based on the results of these studies, the following recommendation was issued in a joint statement by the four continental electrophysiology societies in 2015 (Wilkoff B):

*“It is reasonable to omit defibrillation efficacy testing in patients undergoing initial left pectoral transvenous ICD implantation procedure where appropriate sensing, pacing, and impedance values are obtained with fluoroscopically well-positioned RV leads.”*

As a result, defibrillation threshold testing is less frequently performed, and a strategy which minimizes dependence on human defibrillation testing to establish safety and effectiveness for new devices is necessary.

The Sponsor’s strategy includes a comprehensive set of bench and animal tests that have been conventionally used to evaluate defibrillation efficacy of biphasic waveforms in AEDs with characteristics that are proven and well-understood. These bench and animal studies include:

1. Demonstration of fundamental electrode characteristics required for successful defibrillation (**Impedance and active area meet IEC standards and conventional Anterior-Posterior placement**).
2. Assessment of efficacy by a rigorous study of waveform and dose in animals (Non-inferior to the predicate to establish equivalence): Sponsor Protocol 3337920 *Comparing Efficacy of the ASSURE Wearable Automated External Defibrillator (AED) and the ZOLL LifeVest Defibrillation Waveforms*.
3. Assessment of ASSURE full energy waveform: Sponsor Protocol 3338359 *ASSURE Full Energy Shock Efficacy*.
4. Assessment of ASSURE full energy waveform: Sponsor Protocol 3337766 *Waveform Safety Study*.

In addition, this clinical study is being conducted in humans who are undergoing electrophysiologic procedures for ventricular arrhythmias to demonstrate full energy shock conversion in humans.

Recent, prospective published registry studies of the ZOLL LifeVest provide a relevant reference for establishing a point estimate of defibrillation efficacy for this study. Spontaneous defibrillation efficacy observed in these registry studies is summarized in Table 1.

**Table 1: Spontaneous Defibrillation Efficacy Observed in ZOLL LifeVest Registry Studies**

Registry Study	Number of Subjects	Number of Subjects with Events	Number of Successful Conversions	Conversion Rate
US Registry (WEARIT-II) ( Kutyifa V )	2,000	22	22	100% (C.I. 0.873 – 1.000)
German Registry ( Wäßnig NK )	6,043	94	88	94% (C.I. 0.866 – 0.977)

## PRECLINICAL STUDIES

The following preclinical studies have been completed to demonstrate safety and effectiveness of the waveform in animals:

### **Efficacy of the ASSURE and LifeVest Waveforms at Full-Energy in Swine (Protocol 3338359)**

This prospective block-randomized study compared the efficacy of the ASSURE defibrillation waveform at *full energy output (170J)* in treating electrically-induced VF in a closed chest porcine model of short duration cardiac arrest in comparison to the ZOLL LifeVest defibrillation waveform at *full energy output (150J)*. Six swine were treated for 20 VF episodes each. The VF episodes were organized in 10 blocks, with each block consisting of one shock from each device in random order. Both devices produced a 100% shock success rate in all six animals. This study was designed to measure the difference in success rate between the two devices. Because there was no variation in the data, the lower-bound 95% confidence interval of the difference in success rates (ASSURE shock success rate – LifeVest shock success rate) between the two devices is 0% which meets the non-inferiority criteria.

Overall, this study provides evidence that the ASSURE WCD waveform is non-inferior to the LifeVest waveform in treating VF with full-energy shocks.

### **Efficacy of the ASSURE and LifeVest Waveforms at Reduced Energy Levels in Swine (Protocol 3337920)**

This prospective block-randomized study compared the efficacy of the ASSURE defibrillation waveform at *attenuated energy output (ED50)* in treating electrically-induced VF in a closed chest porcine model of short duration cardiac arrest compared to the currently marketed ZOLL LifeVest defibrillation waveform *attenuated energy output*. Waveform voltages were attenuated to provide greater sensitivity to detect waveform efficacy differences. Probability of defibrillation shock success was compared at three impedance levels (50, 85, and 125  $\Omega$ ). Thirty-six (36) animals were studied.

A summary of the protocol that was followed for each animal is as follows: (1) The ASSURE WCD shock voltage was attenuated to the level that produced an approximate 50% shock success rate (ED50); (2) The LifeVest shock voltage was attenuated by the same percentage; (3) With these voltage levels, ten block-randomized shocks were delivered with each waveform and shock successes and failures were recorded; (4) steps 1, 2, and 3 were repeated at each of the three impedance levels (50, 85, and 125 $\Omega$ ); and

(5) The success rate was calculated for each waveform at each impedance level. The lower-bound 95% confidence interval for the difference between the two devices was compared (ASSURE WCD shock success – LifeVest shock success). The results from this calculation are shown in Table 2, below.

**Table 2: Summary of Reduced Energy Level Study in Swine Results**

Impedance Level	Effect Size	Lower-Bound 95% Confidence Interval	Pass/Fail Limit	Pass or Fail Non-Inferiority Criteria?
50Ω	1.11%	-4.22%	-10%	Pass
85Ω	7.22%	1.38%	-10%	Pass
125Ω	12.50%	7.62%	-10%	Pass

Effect size = ASSURE waveform shock success – LifeVest waveform shock success

Overall, this study provides evidence that the ASSURE WCD waveform is non-inferior to the LifeVest waveform at 50Ω, 85Ω, and 125Ω.

### **Waveform Safety Study in Swine (Protocol 3337766)**

This study compared the safety of the ASSURE WCD waveform at *full energy output (170J)* in swine to a commercially-available external defibrillator (LIFEPAK 12) waveform at 200J. The following protocol was followed for each animal (N = 8): (1) at baseline, blood was drawn and ECG collection was started; (2) five shocks were delivered from the randomly assigned study device; (3) ECG collection continued until at least 1 hour post-shock; (4) 6 hours post shock, another blood sample was drawn and 10 minutes of ECG collected; (5) at least 24 hours post shock, another blood sample was drawn, animal was euthanized, and tissue samples were collected for histological evaluation; and finally (6) the change in biomarkers from the baseline to 6 hour time point and baseline to 24 hour timepoint were analyzed with a student's t-test to see if there was a significant difference between the two devices.

The results from this study met the pre-specified acceptance criteria for the primary endpoints: Change in Troponin I levels from baseline to 6 hours post shock and baseline to 24 hours post shock were not significantly different than LIFEPAK 12 (p=0.45 and p=0.89, respectively); and the mean histopathology injury score difference across all tissue sections was less than 0.4. There were also no significant differences in secondary endpoints including Creatine Kinases (CPK, CK-MB, and CK-MM), CBC and serum chemistry levels and ECG characteristics between the two groups.

Overall, this study provides the evidence that the ASSURE WCD waveform does not cause more injury than the LIFEPAK 12 waveform.

## 6 OVERALL STUDY PLAN

The objective of this study is to obtain human clinical experience with the ASSURE WCD defibrillation waveform in adult subjects. This is a multicenter single arm open label study using the ASSURE WCD defibrillation waveform to convert shockable rhythms (VT and VF). Subjects who consent to participate will be screened for eligibility before the enrollment visit is scheduled. The Investigator will verify eligibility at the time of enrollment.

### Number of Subjects

This is a fixed study design with 20 subjects.

### Study Sites

Subjects will be enrolled at up to 5 clinical sites in the United States where the procedures specified in Inclusion Criterion 3 are performed routinely. There is no minimum or maximum number of subjects that may be enrolled at each site.

### Study Population

Patients who are scheduled for any of the procedures specified in Inclusion Criterion 3 (below).

### Eligibility Criteria

Subjects who meet *all* Inclusion Criteria and *none* of the Exclusion Criteria may be enrolled in the study.

Inclusion Criteria:

1. Males or females, age  $\geq$  18 years
2. Able and willing to provide written informed consent before undergoing any study-related procedures
3. Scheduled for any of the following procedures:
  - a. Electrophysiology study for induction of ventricular arrhythmias
  - b. Non-invasive electrophysiology testing using an existing implantable defibrillator
  - c. ICD replacement procedure during which induction of a ventricular arrhythmia is planned
  - d. Ablation of ventricular tachycardia (patients undergoing ventricular tachycardia ablation in which ONLY a substrate modification approach is planned, with no intention of inducing a ventricular arrhythmia, should *not* be included)

**Exclusion Criteria:**

1. Any condition that by the judgement of the physician investigator precludes the subject's ability to comply with the study requirements
2. Pregnancy
3. Use of mechanical circulatory support (e.g. LVAD, Total Artificial Heart, intraaortic balloon pump or Impella)
4. Documented nonchronic cardiac thrombus
5. Atrial fibrillation or atrial flutter without adequate systemic anticoagulation
6. Critical aortic stenosis
7. Unstable coronary artery disease (CAD)
8. Recent stroke or transient ischemic attack (TIA)
9. Hemodynamic instability
10. Currently implanted Boston Scientific S-ICD (due to location of implant relative to test system)
11. Unstable Angina
12. New York Heart Association (NYHA) Class IV
13. Left Ventricular Ejection Fraction (LVEF) < 20%
14. Any medical condition that by the judgement of the physician investigator, patient participation in this study is not in the best interest of the patient
15. History of difficulty of ventricular arrhythmia induction
16. Amiodarone use within 3 months before the study procedure

**Participation Period**

Individual subject participation is during acute intra-procedural testing only. Subjects can be enrolled only once. Overall study duration will be approximately two months.

**Subject Withdrawals**

Subjects may withdraw from the study for any reason. Subjects may also be removed from the study due to adverse events or Investigator/Sponsor decision. Subjects who are withdrawn from the study will not be replaced.

### **Medical Monitor**

The Medical Monitor (an independent physician not participating as a clinical investigator in the clinical study) will review and assess in conjunction with the Sponsor all AEs considered by the investigator to be at least possibly related to the use of the Test System to determine if they are reportable to the FDA as Unanticipated Adverse Device Effects (UADEs) per the definition in Section 10. The Medical Monitor will also review all Serious Adverse Events considered by the investigator to be at least possibly related to the use of the Test System to verify relatedness and the Serious classification.

### **Sponsor or Regulatory Agency Termination of the Study**

Although the Sponsor intends to complete the study, the right is reserved to discontinue the study at any time for clinical or administrative reasons, or if required by the local regulatory authority.

### **End of Study**

The end of study will be defined as the date of the last visit of the last subject unless open AEs remain in which case the end of study will be when that follow up is completed (the AE is resolved, or the subject is lost to follow up). A summary of the End of Study report will be sent to relevant regulatory authorities and Institutional Review Boards (IRBs) within 6 months of the end of the study.

## 7 STATISTICAL PLAN

### Data Sources

- Case Report Form (CRF) Data will include: Subject ID, Subject Demographics, Confirmation of Eligibility, Cardiac Medical History, Procedure Data (induction attempt number, method, time, arrhythmia type, arrhythmia duration, arrhythmia rate, shock(s) delivered, shock converted), Adverse Events (AEs), Missing data rationale, Deviations and Investigator Signature page.
- EP Study/Testing, ICD changeout, or Ablation procedure documentation including ECG recordings in which conversion was attempted per Section 9 of this protocol, and procedure summary.

### Study Objectives and Endpoints

Efficacy Objective: To evaluate conversion efficacy of the ASSURE WCD Waveform

Primary Endpoint: Estimated cumulative first and second shock VT/VF conversion efficacy  $\geq 94\%$

Secondary Endpoint: First shock conversion efficacy (report only)

Safety Objective: To collect information on adverse events at least possibly related to use of the investigational Test System

Safety Endpoint: Summary of adverse events that are at least possibly related to use of the investigational Test System, including classification of Unanticipated Adverse Device Effects

### Sample Size Considerations

The sample size set for this study has been scaled to obtain human clinical experience in a comparable number of subjects with attempted shock conversion as reported in the published US LifeVest registry study (Kutyifa V), and account for the potential for missing data (e.g., subjects who fail to have a ventricular arrhythmia induced). The sample size is not power-driven.

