### Analysis Populations

The primary endpoint will be analyzed using the data sets as defined below:

1. Intention to Treat (ITT) analysis population will include all subjects who signed informed consent and for whom the study procedure was initiated.
2. Per Protocol (PP) analysis population will include all subjects who met all eligibility criteria, signed informed consent, and for whom the procedure was completed as

specified in section 9 without deviation. The PP analysis population is a subset of the ITT population. If there are no differences in the ITT and PP analysis populations, separate analyses will not be presented.

The determination of any subjects excluded from the PP analysis population will be made prior to locking the study database for final analysis. All safety summaries will be based on the ITT analysis population.

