**Table 3: Steps to Minimize Missing Data for the Primary Endpoint**

Source of missing data	Steps to minimize missing data
Unable to induce a ventricular arrhythmia	History of difficulty of ventricular arrhythmia induction has been specified in the exclusion criteria.
Unable to induce a ventricular arrhythmia with heart rate greater than 150 bpm	History of difficulty of ventricular arrhythmia induction has been specified in the exclusion criteria.
No induction attempted due to change in patient's hemodynamic status	Conditions which place the patient at perceived high risk have been specified in the exclusion criteria.
Rescue shock delivery before either a 1 st or 2 nd shock from the Test System	Protocol training will be provided for the investigator and EP staff.
Pacing or shock therapy from CIED delivered before either a 1 st or 2 nd shock from the Test System	

1. Protocol training will be provided for the investigator and EP staff.

2. Instruction to program CIED therapies OFF is specified in the EP procedure (Section 9).

Pacing from external EP system delivered before either a 1 st or 2 nd shock from the Test System	Protocol training will be provided for the investigator, EP staff and operators
No shock delivered from the Test System due to procedure setup or operator error	

1. Protocol training will be provided for the investigator, EP staff and operators.

2. Operators will be trained on the Test System.

No shock delivered from the Test System due to equipment failure	Each Test System must pass manufacturing test before shipment to the clinical site. In

	addition, the ASSURE WCD Monitor executes a self-test upon boot-up.
--	---

Occurrence of any of these situations shall be reviewed with the Sponsor and the Study PI prior to enrolling any additional subjects at that site. If there still are missing data despite efforts to minimize it the investigator will document on a CRF the reason/rationale for the missing data.

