### **Primary Endpoint Analysis**

The primary endpoint analysis will be performed after all subjects have completed the study and the study database has been cleaned, verified and locked. The data from all clinical sites that participate in this study will be combined so that the target sample size will be available for analysis.

The primary endpoint will be calculated as the ratio of the number of subjects with successful (first or second shock) arrhythmia conversion using the Test System to the number of total inductions attempted with shocks delivered by the Test System in the respective data set. A successful arrhythmia conversion is defined as termination of an induced ventricular rhythm ( $\geq 150$  bpm) by first or second shock from the Test System to a non-shockable rhythm (rhythms other than VT or VF).

Performance criteria will be based on comparison to the published conversion efficacy point estimate of 94% reported for the ZOLL LifeVest (Wäßnig NK), which is the only comparable commercially-available device.

The Pass/Fail criteria will be based on the primary endpoint using the PP analysis population (See Table 3).

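### Does an unquantified missing-data allowance, with a pass/fail table that stops at 17 subjects, leave the primary verdict open?

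*Combined protocol and SAP*

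**What the plan says.** All places are in the combined protocol and SAP.

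- **Number of Subjects (Section 6)** fixes the study at 20. Subject Withdrawals adds that withdrawn subjects are not replaced.
- **Sample Size Considerations (Section 7)** explains that the size was chosen to gain experience "in a comparable number of subjects with attempted shock conversion as reported in the published US LifeVest registry study" and to "account for the potential for missing data (e.g., subjects who fail to have a ventricular arrhythmia induced"). It adds that the number does not come from a power calculation. Table 1 shows 22 subjects with events in that US registry.
- **Study Objectives and Endpoints** sets the primary endpoint: "Estimated cumulative first and second shock VT/VF conversion efficacy" of at least 94%.
- **Primary Endpoint Analysis** gives the source of that figure: "Performance criteria will be based on comparison to the published conversion efficacy point estimate of 94% reported for the ZOLL LifeVest". It also names the deciding data set: "The Pass/Fail criteria will be based on the primary endpoint using the PP analysis population".
- **Table 1** prints the German registry's rate, 88 conversions in 94 subjects with events, as "94% (C.I. 0.866 – 0.977").
- **Table 4** gives rates to one decimal, exact intervals and fail cut-offs for denominators 20, 19, 18 and 17 only. The text beneath it adds an ITT analysis that keeps all 20 subjects and, where data are missing, a tipping-point analysis with best and worst cases.

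**The concern.** The plan says that missing data were allowed for, but a reader cannot find the allowance. Twenty is already below the registry's 22, so there is no visible margin above that reference. The only hint is that Table 4 runs down to 17, which suggests three losses without saying so.

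The table also ends just before the tolerance changes. Down to 17 subjects, one failed conversion still meets the endpoint. At 16 it does not, and no row shows this. That missing row contains 15/16 = 93.75%, which is below 94%, rounds to 94%, and exceeds the registry's unrounded 88/94 = 93.6%. Table 1 uses whole per cents and Table 4 one decimal, and no sentence states the precision of the comparison.

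If this were a true ambiguity, the pass or fail of the study could turn on a convention chosen once the conversions were known. The study is open label, and "The determination of any subjects excluded from the PP analysis population will be made prior to locking the study database for final analysis".

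**Working it through.** **Inputs.** N = 20 (Number of Subjects); criterion: estimate at least 94% (Study Objectives and Endpoints); benchmark counts 88/94 (Table 1); denominators 20 to 17 (Table 4). The documents give no loss rate, so those used in step 4 are assumptions.

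**1. Reproduce Table 4.** Exact (Clopper-Pearson) 95% intervals with the rule x/n ≥ 0.94:

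| Result | Rate | Exact 95% CI | Meets 94%? |
|---|---|---|---|
| 19/20 | 95.0% | 75.1 to 99.9% | yes |
| 18/19 | 94.7% | 74.0 to 99.9% | yes |
| 17/18 | 94.4% | 72.7 to 99.9% | yes |
| 16/17 | 94.1% | 71.3 to 99.9% | yes |

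These agree with the printed rows. So do the four no-failure rows (lower limits 83.2, 82.4, 81.5 and 80.5%) and the four fail cut-offs.

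**2. Extend the same rule below 17.** With f failures among n subjects, the criterion is 1 − f/n ≥ 0.94, that is n ≥ f/0.06.

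- f = 1: n ≥ 1/0.06 = 16.67, so n must be at least 17.
- f = 2: n ≥ 2/0.06 = 33.3, beyond the study size.
- f = 0: always met.

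So one failure is tolerated at 17 to 20 and none at 16 or fewer. At 16: 16/16 = 100.0% (exact 95% CI 79.4 to 100.0%) passes; 15/16 = 93.75% (69.8 to 99.8%) fails. At one decimal 15/16 is 93.8%, also a fail.

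**3. See where another convention would change the verdict.**

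- Whole-per-cent rounding passes anything from 93.5% up, so one failure needs n ≥ 1/0.065 = 15.4, that is 16.
- The unrounded benchmark allows a failure rate of 6/94, so one failure needs n ≥ 94/6 = 15.7, also 16.
- Both differ from the written rule at 15/16 and nowhere else up to n = 20. For example, 14/15 = 93.3% fails on all three readings.

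**4. Chance of landing on that result.** It needs exactly four unevaluable subjects and exactly one failed conversion. Assume independent losses at rate d and true conversion rate p:

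P = C(20,16)(1 − d)^16 d^4 × 16(1 − p)p^15

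The second factor is 0.3795 at p = 94% and 0.3040 at p = 97%.

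| Assumed loss rate d | P(exactly 16 evaluable) | P(15/16), true 94% | P(15/16), true 97% |
|---|---|---|---|
| 5% | 0.0133 | 0.5% | 0.4% |
| 10% | 0.0898 | 3.4% | 2.7% |
| 15% | 0.1821 | 6.9% | 5.5% |
| 20% | 0.2182 | 8.3% | 6.6% |

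The first factor is largest at d = 4/20 = 20% (0.2182). The second is largest at p = 15/16, where it equals (15/16)^15 = 0.3798. The product, 0.2182 × 0.3798 = 0.083, is therefore the ceiling over all loss rates and true rates.

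**5. What a reader would see in that case.** With 15 conversions in 16 and four subjects missing, the best- and worst-case bounds over all 20 are 19/20 = 95% and 15/20 = 75%. The analyses already planned under Table 4 would show that spread beside the PP result.

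**The case for a change.** The best case for a change runs as follows. Table 4 is headed as the pass/fail criteria, so a reader may take it as complete. Fewer than 17 evaluable subjects is foreseeable: PP status requires a procedure without deviation, Section 9 lists several likely deviations, and subjects who cannot be induced have no Test System shock to count. At assumed loss rates of 5, 10, 15 and 20%, the chance of 16 or fewer evaluable is 1.6, 13.3, 35.2 and 58.9%. With exactly 16, the reading matters: at a true rate of 97% the chance of passing is 61.4% if 15/16 fails and 91.8% if it passes. A sentence and a table row would cost nothing.

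What stands is that the allowance is not quantified and the table does not display the drop from one tolerated failure to none. The rest does not carry. The rival readings have no footing in the text: the threshold is given as 94% in both places that state it, no section sets 93.6%, and the only table of this study's own results uses one decimal. The whole-per-cent figures describe cited registries. The 61.4% against 91.8% contrast holds only given exactly 16 evaluable, and only if someone departs from the written inequality.

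The sample size argument is also weaker than it looks. The plan promises a number comparable to the registry's, not 22 plus a margin, and with no power target there is no evaluable count to protect. Three losses is an inference from where the table ends; writing it in as the sponsor's allowance would attribute a basis the plan does not claim. Choosing PP exclusions when outcomes are known is a separate question that a rounding sentence would not settle. Table 3 addresses the losses themselves: it lists preventive steps, and each occurrence "shall be reviewed with the Sponsor and the Study PI prior to enrolling any additional subjects at that site".

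**Conclusion.** No change follows. This is missing detail that an analyst fills by applying the stated criterion: an estimate of at least 94% gives one answer at every denominator, every printed row of Table 4 is right, and 15/16 fails both unrounded and at the table's one-decimal precision. A row for 16 would write down what the rule already implies and would alter no result. Even the one case where another convention would differ has a chance of 0.4 to 6.6% at a true rate of 97% with assumed losses of 5 to 20%, and never above 8.3%. Those figures rest on independent losses and conversions and on loss rates that the documents do not give. The conclusion does not depend on them, because the verdict at 15/16 is fixed by the criterion.
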